Sensory Integration of Auditory and Visual Cues in Diverse Contexts

Study Protocol

June 1st, 2020

NCT04479761

The same sample of adult participants (18 or older) will be recruited to study both specific aims. All participants will have normal or corrected to normal vision and no peripheral neuropathy or other neurological conditions. Control participants will be recruited from the NYU community, and registry of alumni, local fitness centers and local senior centers. The two patients' groups will be recruited from the Ear Institute of Mount Sinai.

Group 1: Unilateral peripheral vestibular hypofunction and normal hearing, e.g., vestibular neuritis. Potentially eligible participants with a functional complaint of head motion provoked instability or dizziness affecting their functional mobility and quality of life will be identified by key personnel and additional staff at the Ear Institute during their standard clinical evaluation. They will present with at least one positive finding indicating unilateral vestibular hypofunction on the following clinical tests: head thrust, subjective visual vertical and horizontal, post head shaking nystagmus, spontaneous and gaze holding nystagmus⁸⁴ in addition to a score of at least 16 (mild handicap) on the Dizziness Handicap Inventory (DHI).⁷¹ Unilateral peripheral vestibular hypofunction will then be confirmed by the meeting at least one of the following diagnostic criteria:^{2,85}

- 25% or above unilateral weakness on caloric testing⁷⁰;
- Low gain on vHIT <.8;⁸⁶
- Ocular Vestibular evoked myogenic potential (oVemp) amplitude asymmetry greater than 34%;
- Cervical (cVemp) amplitude asymmetry greater than 40%.

Patients will be excluded if they are diagnosed with an unstable peripheral lesion, e.g., Meniere's Disease, Perilymphatic Fistula, Superior Canal Dehiscence, or Acoustic Neuroma.

Group 2: Acquired moderate/severe/ profound unilateral hearing loss no evidence of retrocochlear pathology on MRI and no active complaint of dizziness (DHI score < 16)⁷¹ or imbalance.⁷² Hearing loss will be defined as having an unaided pure-tone average (PTA) of hearing thresholds at 0.5, 1, 2, and 4 kHz in the affected ear > 40 dB HL and normal hearing in the contralateral ear. Normal hearing will be defined as an unaided PTA < 26dB HL (0.5–4 kHz) bilaterally. This is considered healthy hearing according to the World Health Organization.^{20,73} For those above 65 years of age, symmetric age-related hearing loss (ARHL) in the mild hearing loss range, specifically an unaided PTA < 40 dB (0.5-4KHz) will be included.⁷⁴ Given that ARHL has been reported to affect 67% of adults over the age of 70 and 80% of adults over the age of 85^{75,76}, this criterion will allow for a better representation of the aging population. We will adjust for the presence of ARHL in the statistical analysis.

Exclusion criteria for all groups will include a medical diagnosis of peripheral neuropathy; lack of protective sensation based on the Semmes-Weinstein 5.07 Monofilament Test;⁸⁷ visual impairment above 20/63 (NYS Department of Motor Vehicle cutoff for driving) on the Early Treatment Diabetic Retinopathy Study (ETDRS) Acuity Test that cannot be corrected with lenses; conductive hearing loss or air bone gap; pregnancy; any neurological condition interfering with balance or walking (e.g. multiple sclerosis, Parkinson's disease, stroke); acute musculoskeletal pain at time of testing; currently seeking medical care for another orthopaedic condition; and inability to read an informed consent in English. Control participants will be excluded for any positive finding on the vestibular diagnostic testing or history of vestibular symptoms (dizziness, vertigo).

The following procedures will be done:

Diagnostic Session (Ear Institute, could be split into 2): First, we will obtain a written informed consent. Then participants will complete a short demographic questionnaire noting age, gender, height, weight, ethnicity and race, as well as confirming the absence of exclusion criteria from self-reported medical history. Next participants will go through vestibular and auditory testing done by an audiologist at the Ear Institute. These tests are part of a standard battery for patients with vestibular complaints and include:

Videonystagmography (VNG): The VNG caloric test requires the participant to wear goggles that allow careful monitoring of eye movement in response to hot and cold air placed in the ear canal.

[figure not shown]
Audiogram: The participant wears headphones and is asked to identify sounds at different frequencies and repeat simple words.

Video Head Impulse Test (vHIT): The vHIT requires the participant to wear special goggles and focus on a target on the wall. The examiner will move that participant's head right, left, up, down and diagonal while he/she keeps their eyes on the target.

The session is expected to take 2 hours.

Postural Control session (NYU Physical Therapy Department, Arthur J. Nelson Jr., Human Performance Laboratory, could be split into 2): Participants will complete 4 self-reported questionnaires as described under 'materials' below (they can complete it at home prior to the session as well if they prefer). The participants will be wearing a virtual reality headset (HTC Vive) and bluetooth-connected headphones (Bose). They will complete a series of standing tasks while observing a virtual display and listening to sounds. They will be asked to stand with their feet hips-width apart. The variations of visuals and sounds are explained in Table 1 below. All conditions will be randomized. Sounds will be displayed at the highest level that is comfortable to the participant. Scenes are 60 seconds long. We have a total of 12 combinations: 2 environments (stars, subway) X 2 visuals (moving, static) X 3 sounds (moving, none, static) and each combination will be repeated 3 times for a net testing time of 36 minutes. Including rest breaks, total testing time is expected to take no longer than 2 hours could be completed over 2 sessions. For aim 1, we will assess the significance of contrasts between no sounds / dynamic sounds for the different visual conditions and groups. For aim 2, the same will be done for contrast between no sounds / static sounds.

Table 1. Protocol for the 2 specific aims.

The environment	Visuals	Sounds
An abstract display of star wall 	Static stars Moving stars: 0.2 Hz, 0.032m, Anterior-Posterior (AP)	No sound Static White Noise Moving Sound: white noise circling around the participant
A salient subway station 	Static avatars and train Avatars are moving from front and back at a speed of 0.71–2.45m/s, flow of trains	No sound Static White Noise Detailed natural environmental sounds with high density of footsteps and train sounds

The following materials will be collected:

Diagnostic Outcomes:

1. Caloric testing: Unilateral weakness percentage
3. Audiogram: decibel hearing threshold across various frequencies (pure-tone average).
4. vHIT: Vestibulo-Ocular Reflex Gain

Self-reported Questionnaires:

1. The Dizziness Handicap Inventory (DHI): Designed to identify difficulties that a patient may be experiencing because of his/ her dizziness.⁴⁵ We will record the total score as well as scores on the Functional, Physical, and Emotional sub-scales.

2. The Activities-Specific Balance Confidence (ABC): A subjective scale where subjects are asked to rate their balance confidence from 0-100% performing 16 different tasks.⁴⁵
3. The Speech, Spatial and Quality of Hearing 12-item Scale (SSQ12): A valid, short version of the original SSQ which provides insights day-to-day hearing loss impact.⁷⁹
4. The Simulator Sickness Questionnaire: This 15-item questionnaire will be administered as a structured interview every rest break to monitor participants' symptoms.⁸⁰ The number of none, slight, moderate or severe symptoms will be recorded.

Physical Outcomes:

Center of Pressure position in the anterior-posterior and medio-lateral directions will be recorded at 100 Hz from a laboratory force platform that is embedded in the floor under the participants' feet. Directional Path, and sway area will be calculated in a custom-designed Matlab software.

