# **Sensory Integration of Auditory and Visual Cues in Diverse Contexts**

## **Statistical Analysis Plan**

**June 1st, 2020**

**NCT04479761**

For each of measure of interest and for each environment (stars, subway), we will fit a linear mixed effects model. Each model will include main effects of group, visual condition, and auditory condition, as well as all two and three-way interactions. The models will also control for age. For aim 1, we will assess the significance of contrasts between no sounds / dynamic sounds for the different visual conditions and groups. For aim 2, the same will be done for contrasts between no sounds / static sounds. These models estimate the difference in visual weighting and reweighting between the groups, maximizing the information we can obtain from the data by accounting for the inherent multi-level study design (person, conditions, repetitions). Since each person completes various trials for each condition, the linear mixed effects model accounts for these sources of variability. *P*-values for the fixed effects will be calculated using the Satterthwaite approximation for the degrees of freedom for the T-distribution.

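### The protocol promises adjustment for age-related hearing loss, but the model in the SAP has no term for it

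*Protocol*

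**What the plan says.** The hearing criteria stand in the Group 2 paragraph of the protocol. The general rule is "Normal hearing will be defined as an unaided PTA < 26dB HL (0.5–4 kHz) bilaterally". For people above 65 it is relaxed: "symmetric age-related hearing loss (ARHL) in the mild hearing loss range, specifically an unaided PTA < 40 dB (0.5-4KHz) will be included". The reason given is representation of older people, since "ARHL has been reported to affect 67% of adults over the age of 70". The paragraph ends with the commitment "We will adjust for the presence of ARHL in the statistical analysis". Group 2 itself is defined by a pure-tone average (PTA) "in the affected ear > 40 dB HL and normal hearing in the contralateral ear".

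The SAP is a single paragraph with the same date. It gives the model as "Each model will include main effects of group, visual condition, and auditory condition, as well as all two and three-way interactions", and then adds "The models will also control for age". The test under the first aim is worded in the SAP as follows: "we will assess the significance of contrasts between no sounds / dynamic sounds for the different visual conditions and groups"; aim 2 does the same with static sound. The SAP names no hearing variable. The protocol's Postural Control session repeats the contrasts of both aims and adds no covariate.

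**The concern.** The two documents describe different analyses. The protocol widens eligibility on a hearing criterion and offers statistical adjustment as the safeguard; the document that specifies the analysis does not carry that safeguard. Because both bear the same date, neither supersedes the other.

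The omitted variable is not incidental. Both aims ask whether sound changes postural sway and whether that change differs by group, so hearing status is a plausible modifier of the effect under study. Nothing secures equal ARHL shares across groups: controls come from community sources that include senior centers and fitness centers, patients come from one clinic, and no age matching is stated. With the form of the adjustment unwritten, it could also be chosen after the data are seen.

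**Working it through.** The plan states no figure to reproduce here. The check compares the texts, counts terms and asks which terms can reach the contrasts.

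**1. Terms in the SAP model.** There are three groups (controls, Group 1, Group 2), two visual conditions and three sound conditions. With all interactions this gives 3 × 2 × 3 = 18 cell parameters. Adding age gives 19. None is a hearing term.

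**2. Can age or group stand in for ARHL?** ARHL is defined by PTA, not by age. On the protocol's figure, 100% − 67% = 33% of people over 70 do not have it. The 67% carries no severity limit, while the trial excludes a PTA of 40 dB or more under the ARHL allowance. If a fraction *s* of over-70s is ineligible for that reason, the ARHL share among those eligible is (0.67 − *s*)/(1 − *s*). For an assumed *s* of 0 to 0.30:
- *s* = 0: 0.67, so 33% without ARHL;
- *s* = 0.30: 0.37/0.70 = 0.53, so 47% without ARHL.

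People of the same age therefore differ in status. The group label does not record it either.

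**3. Where must the term sit?** For person *i* in group *g*, under visual condition *v* and sound *a*, the model with ARHL added as an ordinary covariate is

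Y = μ(g,v,a) + β·age + γ·ARHL + person effect + error.

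The sound minus no-sound difference for the same person and visual condition is

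μ(g,v,a) − μ(g,v,none) + error.

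Age, ARHL and the person effect all cancel. With complete, balanced data, an ARHL main effect leaves the contrasts of both aims unchanged, and so does the SAP's age term. Only ARHL × auditory and ARHL × visual × auditory terms survive the subtraction. The second is needed because the contrasts are read separately by visual condition; ARHL × visual is its lower-order companion.

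**4. Added terms.** Main effect 1, × visual 1, × auditory 2, × visual × auditory 2: 1 + 1 + 2 + 2 = 6, and 19 + 6 = 25.

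**5. Size of bias.** Let the sound effect be δ without ARHL and δ(1 − *r*) with it, and let the ARHL shares in two groups be *p*₁ and *p*₂. The unadjusted difference between groups in the sound contrast is then off by −δ·*r*·(*p*₂ − *p*₁). This is zero if *r* = 0 or *p*₁ = *p*₂. The documents give neither *r* nor the shares, and no sample size or age distribution, so the expression cannot be evaluated for this trial.

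**The case against.** **The promise, read plainly, is only for a covariate.** The protocol mentions no interaction, and the SAP treats age as a simple covariate. On that reading, honouring the promise would change sway levels but, by step 3, not the contrasts of either aim. This stands. The mismatch between the documents and the possible bias are separate matters: the bias comes from omitted interactions, which neither document explicitly promises.

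**The SAP need not be read alone.** It does not call its list exhaustive and does not withdraw the protocol's commitment. This stands in part: the adjustment is lost only if the analyst works from the SAP by itself. Even an analyst who reads both documents finds no definition of the variable and no role for it.

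**Age was meant to cover ARHL.** This does not stand, for the reasons in steps 2 and 3.

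**A reader might infer that the group comparisons are biased by a known amount.** The documents do not support this. As illustration only, suppose the share of people over 70 is 10% in one group and 40% in another, ARHL affects 53% to 67% of those eligible, and it removes 25% to 50% of the sound effect. The bias would run from 0.30 × 0.53 × 0.25 = 0.04 to 0.30 × 0.67 × 0.50 = 0.10 of the sound effect. Every input except the 67% is assumed. Equal shares or an unchanged response gives zero, and a stronger response with ARHL reverses the sign. Setting the volume to each person's comfort limit may also shrink any effect.

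**A reader might also infer that age-by-condition interactions are required.** The SAP's age term contradicts nothing in the protocol, so they are a matter of choice.

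**Group 2 coding is partly answered.** Symmetry and bilateral normal hearing cannot be applied literally to someone with one ear above 40 dB HL, but the contralateral ear is the natural one to use. It still has to be written down.

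**Conclusion.** The inconsistency is real and should be fixed. An adjustment that the protocol promises has no place in the model stated in the SAP, and neither age nor group supplies it. Confidence is high for that textual point and does not extend to any figure for bias, which remains unknown and may be zero. That only interactions with auditory condition can adjust the contrasts of the aims follows from the algebra and assumes complete, balanced data; with missing trials the cancellation need not be exact.

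**What to change.** Add to the SAP wording such as:

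> Models will include an ARHL indicator (1 if above 65 years with better-ear PTA of 26 to < 40 dB HL, using the contralateral ear in Group 2; otherwise 0) as a main effect and with its interactions with visual condition, auditory condition and visual × auditory condition. The ARHL effect is assumed common across groups. A sensitivity analysis will be restricted to participants with better-ear PTA < 26 dB HL.

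Age-by-condition interactions can be a further, optional sensitivity analysis. If the sponsor prefers age alone, both documents should say so with the reason, recognising that an age main effect does not adjust the sound contrasts either.

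**Cost.** The change is SAP wording and one coding rule; the audiogram PTA is already among the Diagnostic Outcomes. The model gains 6 parameters. ARHL and age are partly collinear (correlation about 0.54 in simulated data under assumed ages). In simulation with an assumed 25 to 80 people per group, a larger model that also had age interactions widened the standard error of a group difference in a sound contrast by about 0% to 4% on average. The 25-term model is nested in that one, so its cost should be no greater.

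Some groups may hold few people with ARHL. With an assumed 10% over 70 and 60% of them with ARHL, the share is 0.10 × 0.60 = 6%. The chance that such a group contains nobody with ARHL is then 0.94^25 = 21% at 25 people, 8% at 40 and 0.7% at 80. The adjustment in that group would rest wholly on the other groups, which is why the common-effect assumption must be stated and the restricted analysis reported.

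### Group 2 must be free of any active complaint of imbalance but controls need not be, so the two groups are screened unequally on a trait close to the sway outcome

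*Protocol*

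**What the plan says.** Three sets of criteria in the protocol bear on this point.

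- **Group 2.** Entry requires "no active complaint of dizziness (DHI score < 16)⁷¹ or imbalance". Dizziness and imbalance are listed as two separate complaints, and the DHI cutoff is attached to dizziness.
- **Controls.** The sentence specific to them reads: "Control participants will be excluded for any positive finding on the vestibular diagnostic testing or history of vestibular symptoms (dizziness, vertigo". It does not mention imbalance.
- **All groups.** The list opens: "Exclusion criteria for all groups will include a medical diagnosis of peripheral neuropathy; lack of protective sensation based on the Semmes-Weinstein 5.07 Monofilament Test". It goes on to uncorrectable visual impairment, "any neurological condition interfering with balance or walking", and "acute musculoskeletal pain at time of testing; currently seeking medical care for another orthopaedic condition", among other items.

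On recruitment: "Control participants will be recruited from the NYU community, and registry of alumni, local fitness centers and local senior centers".

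The outcomes come from center of pressure (Protocol, Physical Outcomes): "Directional Path, and sway area will be calculated in a custom-designed Matlab software". The SAP fits, for each measure and environment, a linear mixed model with group, visual condition, auditory condition and all their interactions, controlling for age. Both aims are tested through contrasts of no sound against dynamic sound (aim 1) or static sound (aim 2), by visual condition and group.

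**The concern.** A complaint of imbalance is a self-report of something very close to what the force platform measures. Group 2 is selected to be free of it and the control group is not. Part of any Group 2 versus control difference in sway could then reflect who was let in rather than hearing loss.

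If people who report unsteadiness do sway more, the missing screen can only add less steady people to the control side. On its own that lowers the Group 2 minus control difference. A real increase in sway with hearing loss would look smaller, and Group 2 could even look steadier than controls.

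The planned adjustment does not deal with this. The SAP names age, and the protocol adds age-related hearing loss. Neither measures steadiness, which varies among people of the same age and hearing.

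**Working it through.** **Step 1: the eligibility text, side by side.** Take one candidate: feels unsteady, has no history of dizziness or vertigo, has normal vestibular tests, and has none of the conditions in the all-group list.

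| Criterion | Group 2 candidate | Control candidate |
|---|---|---|
| All-group exclusions | passes | passes |
| Dizziness or vertigo | passes | passes |
| Positive vestibular test | no such exclusion written | passes |
| Active complaint of imbalance | **excluded** | **no criterion** |

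The all-group exclusions apply equally to both groups. They narrow the set of people concerned but leave the last row unequal.

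**Step 2: the DHI.** Group 2 must have no active dizziness complaint, with DHI below 16. Controls are excluded for any history of dizziness or vertigo, which is at least as strict. The protocol also describes the DHI as measuring difficulty caused by dizziness, so it is not aimed at a person who is unsteady without dizziness. The only item missing for controls is imbalance.

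**Step 3: effect on the group difference in sway.** Let a share *q* of controls be unsteady, with mean sway higher by *d*. Take as target the difference D between Group 2 and controls screened the same way.

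Expected observed difference = D − *q·d*

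If *d* happened to equal D, the observed difference would be (1 − *q*) of the target: 95% at *q* = 5%, 90% at 10%, 80% at 20%.

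If instead unsteady controls sway *k* times as much, mean control sway is multiplied by 1 + *q*(*k* − 1):

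| Assumed *q* | Assumed *k* | Rise in mean control sway |
|---|---|---|
| 10% | 1.25 | 0.10 × 0.25 = 2.5% |
| 20% | 1.5 | 0.20 × 0.5 = 10% |
| 30% | 2 | 0.30 × 1 = 30% |

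The last row is an extreme, not a typical case, given the all-group exclusions. The SAP states no transformation, so the arithmetic mean is the relevant one. Were sway analysed on the log scale, the multiplier would be *k* to the power *q*, which is milder: 1.5 to the power 0.2 = 1.084, or 8.4%, in the middle row.

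**Step 4: effect on the sound contrasts.** Let *g* be the extra change from no sound to sound in unsteady controls, beyond that in steady ones. The bias in the group difference of contrasts is −*q·g*.

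- If unsteadiness adds the same amount in every condition, *g* = 0 and the bias is zero.
- If the response is proportional to sway, the control contrast on the untransformed scale is multiplied by the same 1 + *q*(*k* − 1). On the log scale it would cancel.

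The same reasoning holds for static against moving visuals.

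**Inputs.** *q*, *k*, *d* and *g* are all assumptions. The documents give no sample size, standard deviation or effect size, so no power figure can be derived from them.

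**The case against.** The strongest reply is that this is a small gap in a fairly thorough screen. The all-group list already removes several main causes of poor balance: neuropathy, lost protective sensation, poor vision, neurological disease affecting balance, acute pain and current orthopaedic care. This stands. A reader might infer that controls are screened only for vestibular findings and dizziness, so that people with poor balance enter freely. The documents do not support that; what is left is a residual group with unexplained unsteadiness.

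Second, the aims are tested by within-person sound contrasts, and a constant shift in sway cancels from these. This also stands, and it limits the point. It does not dispose of it: the models include a group term as well, and nothing in the documents shows that unsteady people respond to sound and moving visuals by the same absolute amount as steady people.

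Third, the net direction is open. Controls come from "local fitness centers and local senior centers", and fitness-center recruits could make controls steadier and enlarge a difference. A reader might infer that the plan will hide a group difference in sway. That is one possibility and not something the documents show. Uncertain direction is still no reason to screen the two groups differently.

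Fourth, a study team might read imbalance into the term for vestibular symptoms. But the parenthesis names only dizziness and vertigo, and the Group 2 criterion treats imbalance as separate.

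Finally, the ABC balance-confidence scale is collected, so the groups can be compared on it. This helps with description, but the ABC is neither an eligibility criterion nor a named covariate.

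**Conclusion.** The concern holds in a narrow form. The text screens Group 2, but not controls, for an active complaint of imbalance, and age adjustment cannot repair that. The group main effect of Group 2 versus control can be biased by *q·d*. The contrasts that carry both aims are biased only by *q·g*, which is zero if unsteadiness shifts sway equally in all conditions.

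The documents do not allow either quantity to be computed. The 2.5% to 10% rise in mean control sway is an illustration that rests wholly on assumed shares and ratios, and it concerns mean sway and not the aims' contrasts. A reader might also infer that controls are screened more loosely for dizziness because no DHI cutoff is given for them. They are not, since any history of dizziness or vertigo already excludes them.

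This is a minor point, worth acting on because the remedy is cheap and removes the selection difference at its source.

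**What to change.** Add *or an active complaint of imbalance* to the list of control exclusions. Put the question to controls in the same words as to Group 2; the documents do not set out that wording, so the protocol should fix one form for both groups. No DHI cutoff is needed for controls.

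If controls are already enrolled, ask them the same question where possible and repeat the group comparisons without those who report imbalance, as a sensitivity analysis.

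The cost is one eligibility clause and one screening question, with no change to testing or to the models. The downside is a few more control screen failures, mainly among older recruits.
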